9.4. Data Sources

The IMS[®] Disease Analyzer, a German longitudinal patient-level database will be used as data source for the Flupirtine utilization study.

IMS[®] Disease Analyzer

IMS[®] Disease Analyzer is a database which continuously receives anonymised data reported from approximately 3,000 office-based physicians* (including specialists such as cardiologists, gynaecologists, neurologists, orthopaedists, or urologists) representing approximately 2.4% of all practices* in Germany. The database contains longitudinal data from more than 11 million observational profiles documented over the last 3 years.

The data are generated directly from the electronic medical records of the panel physicians' practice via standardized interfaces and provide daily routine information on patients' diseases and therapies. The main parameters routinely collected in the IMS[®] Disease Analyzer database are presented in Table 1. The lag time of data availability is 6 weeks.

The IMS[®] Disease Analyzer PCP panel consists of 1,141 PCPs (general practitioners [GPs] and internists without subspecialty) and 177 orthopaedists selected using a pre-specified random plan as described by Becher et al. (2009) in their paper verifying the validity and representativeness of the IMS[®] Disease Analyzer patient database in Germany⁸.

* No personal data but exclusively anonymous information (in accordance with § 3 Abs. 6 "Bundesdatenschutzgesetz" – German Federal Data Protection Act).

Table 1: Variables included in the IMS[®] Disease Analyzer database

Category	Nature of data	Variables
Patient data	Characteristics	Age, sex, insurance(private or SHI insured)
	Diagnoses	Date of diagnosis, ICD-10, original text, co-morbidity, laboratory tests and results
	Therapy	Date of visit, product and quantity, molecule, ATC, dosage scheme, co-prescription

The German IMS[®] Disease Analyzer database has been previously used to answer a wide range of research questions^{9,10,11,12}. In addition, the IMS[®] Disease Analyzer database is used by the European Medicines Agency (EMA) as one of its resources for answering research questions.

A preliminary investigation showed that most of patients who had received Flupirtine prescriptions in the IMS[®] DA were documented in the PCP panel and the orthopaedist panel (about 95%). For the time period from August 2011 to July 2013 nearly 54,000 patients with at least one Flupirtine prescription were recorded in the DA database including about 39,000 Flupirtine patients treated by PCPs and about 15,000 Flupirtine patients treated by orthopaedists. The current DUS will therefore be based on data from the PCP panel and the orthopaedist panel.

9.5. Study size

All patients in the PCP and orthopaedist panel of the IMS[®]DA fulfilling the selection criteria will be considered for the study.

A preliminary count of patients treated with Flupirtine over a 12-month period (July 2013 to June 2014) gave the sample sizes for the selected IMS[®] DA panels (presented in Table 2). As acute pain treatment has no seasonal impacts, the 12 months period and not a calendar year period is acceptable for feasibility appraisal.

Table 2: Number of patients with flupirtine-containing prescriptions in the IMS[®] Disease Analyzer from July 2013 to June 2014

IMS [®] DA Panel	Number of Flupirtine patients	Number of Flupirtine patients with at least 12 months history	Number of Flupirtine patients with at least 12 months history (25% reduction)
PCP	14,743	11,284	8,463
Orthopaedist	4,635	1,821	1,365

Taking into account the sample sizes and a further 25% reduction for a hypothetical decrease in Flupirtine prescriptions over the planned observation period compared to the period evaluated in 2014, we expect that the minimum number of Flupirtine patients available for the analysis will be not lower than about 8,400 and 1,300 patients in the DA PCP and orthopaedist panel, respectively. The more data are available, the higher the level of confidence on any estimates, i.e. the smaller the width of the 95% confidence interval.

Similar Flupirtine patient counts for the DA database are expected for the 12-month selection window of the Flupirtine DUS.

The study size of the Flupirtine DUS is expected to range from approximately 1,300 Flupirtine patients in the orthopaedist panel of the IMS[®] DA database. The study size is based on the number of patients with Flupirtine prescriptions in the 12-month period from July 2013 to June 2014, so the study size of the planned 12-month patient selection window in the Flupirtine DUS may be slightly different.

The 12-month patient selection window is considered to be sufficient to provide representative for prescribing practices during the routine clinical use of flupirtine-containing medicinal products in Germany.

9.6. Data management

The study will be conducted according to IMS Health standard operating procedures (SOPs) of IMS Health. Data sets extracted from the database will be stored to allow future analysis if needed.

9.7 Data analysis

9.7.1 General remarks

Data from specialist panels will not be combined. The data will be analysed separately by panel (PCP and orthopaedist panel) and for the period before and after SmPC review.

All analyses will be stratified by incident and prevalent users.

Study tables will reference the data source used for each set of results. The data will be presented graphically where useful.

The statistical unit will be the patient (for information such as demographical and clinical characteristics, medical history, contraindications) and the Flupirtine prescription (for information such as indication, number of prescriptions, recommended treatment duration, concomitant drug prescriptions).

The statistical analysis will be done descriptively. Missing values will be reported as missing and no imputation will be conducted. Descriptive tables will be compiled for all variables. Continuous variables will be presented with counts, means, medians, standard deviations, and minimum and maximum values. Categorical variables will be presented in frequency tables. Rates and 95% confidence intervals will be provided when relevant.

Data will be analysed using the statistical software SAS (SAS Institute Inc., Cary, USA) with version 9.3 or above.

All results will be presented in tables. In addition, parameters addressing the primary objectives and eligible for a comparison of time periods (assessment period and reference period) with respect to the effect of risk minimisation measures (for example flupirtine treatment duration) will be presented graphically e.g. by displaying plots or bar charts.

The following section will describe the analyses and definitions used for the DA (**IMS[®] Disease Analyzer**) database.

9.7.2 EMR data (IMS® Disease Analyzer) – PCP and orthopaedist panel

Prevalent and incident patients

The entire analysis will be stratified by incident patients - defined as new patients, if no flupirtine containing products were dispensed for at least 12 months previous to the first Flupirtine treatment within each study period, and prevalent patients - defined as patients with at least one prescription of Flupirtine products 12 months prior to index date of first prescription within analysis period.

Flupirtine patients by specialty, by region (East/West Germany) and number of patients in the office

The number of Flupirtine patients per specialty will be analyzed, adding the region (East/West Germany) and overall number of patients within the office

Analyses:

- Number of Flupirtine patients per specialty including region (East/West Germany) and number of patients in the office

9.7.2.1 Patient characteristics of Flupirtine treated patients

The patient characteristics (age, gender, insurance private or SHI) of Flupirtine patients will be described.

- Number of patients within following age groups:
 - < 18 years
 - 18 to 29 years
 - 30 to 39 years
 - 40 to 49 years
 - 50 to 59 years
 - 60 to 69 years
 - 70 years and older

Analyses:

- Number and percentage of Flupirtine patients per age group, gender, insurance status(private or SHI insured)

Indication for flupirtine prescription

In order to describe the indication for flupirtine drugs all diagnoses related to the flupirtine prescriptions will be analysed.

- All diagnoses documented on the prescription of flupirtine will be defined as principal diagnosis.

As not for all prescriptions principal diagnoses will be available, additionally the following approaches will be chosen:

- If there is any disease associated with acute pain (Annex 3-ii) recorded in a time frame of 2 weeks around the date of prescription, this will be defined as associated diagnosis.
- If there is any disease associated with acute pain (Annex 3-ii) recorded in a 12 months history before the date of prescription, this will be defined as co-morbidity.

Principal diagnoses, associated diagnoses and co-morbidities will be analysed separately.

The findings of principal diagnoses will be grouped by diagnosis according to ICD-10 codes (selection of codes see Annex 3) including diseases associated with acute pain and chronic pain.

Analysis:

- Number and percentage of prescriptions, stratified by diagnosis (only principal diagnoses)
- Number and percentage of prescriptions associated with acute pain (principal diagnoses, associated diagnoses and co-morbidities)
- Number and percentage of prescriptions associated with chronic pain (only principal diagnoses)

Contraindication for the use of NSAIDs or weak opioids

The patients' history will be evaluated for medical events referencing to contraindications for NSAIDs or weak opioids (such as myocardial infarction or stroke) for a timeperiod of 12 months prior to first prescription of Flupirtine. Only patients with a history of at least 12 months will be included in this analysis.

Analyses:

- Number and percentage of patients identified as contraindicated of NSAIDs/weak opioid treatment (such as myocardial infarction or stroke)

Long-term medications leading to contraindications for Flupirtin

A therapy duration exceeding 14 days will be considered as long-term treatment within a year time span. A long-term treatment known to lead to contraindications for the use of Flupirtine will be analyzed

Analyses:

- Number and percentage of long-term therapies leading to contraindication of Flupirtine

Concomitant diseases of Flupirtine patients

Diseases are assumed to be concomitant, if prescription issued prior or after 2 weeks to Flupirtine treatment within study period.

Analyses:

- Number and percentage of patients with concomitant diseases during observation period, grouped by ICD codes

Therapies related to Flupirtine treatment

Patients treated with Flupirtine will be monitored by analyzing all co-prescriptions within the observation window of 12 months prior to Flupirtine treatment start, grouped by diagnosis according to ICD-10 codes [selection of codes see Annex 3 (ii)].

Analyses:

Number and percentage of patients receiving co-medication during 12 months prior to Flupirtine treatment start grouped by diagnosis according to ICD-10 codes [selection of codes see Annex 3 (ii)].

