9.7.2.4 Comparison of the patient/prescriptions of the two observational periods

The comparison of the patients/prescriptions of the two observational periods (assessment period and reference period) based on IMS[®] Disease Analyzer data will consider the following parameters. The comparisons will be performed separately by physician panel and will be stratified by incident and prevalent users:

- Number and percentage of patients with any diagnosis of disease contraindicated for NSAIDs or weak opioids
- Number and percentage of prescriptions with diagnosis associated with acute pain
- Number and percentage of patients with single and repeated flupirtine prescriptions within the defined time period
- Number and percentage of prescriptions with LFT monitoring during flupirtine treatment
- Length of treatment episodes
- Number and percentage of patients with at least one treatment episode longer than 14 days (based on DDD)

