Annex 3. Additional information

i. List of flupirtine-containing medicinal products in Germany in 2014

Dolokadin 400mg Tabletten Retard
Flupirtinmaleat Winthrop® 400 mg Retardtabletten
Flupirtinmaleat Winthrop® 100 mg Hartkapseln
Flupigil® 100 mg Hartkapseln
Katadolon® S long
Katadolon®
Katadolon® Zäpfchen
Katadolon® Kinderzäpfchen
Katadolon® inject
Trancolong®
Trancopal® dolo
Trancopal® dolo Suppositorien

ii. Diseases associated with acute pain, acute pain episodes, acute pain exacerbations (selection)

G20-G26 Extrapyrarnidal and movement disorders

- G20 Parkinson disease
- G21 Secondary Parkinsonism
- G22 Parkinsonism in diseases classified elsewhere
- G23 Other degenerative diseases of basal ganglia

G35-G37 Demyelinating diseases of the central nervous system

- G35 Multiple sclerosis

G40-G47 Episodic and paroxysmal disorders

- G44 Other headache syndromes

M15-M19 Arthrosis

- M15 Polyarthrosis
- M16 Coxarthrosis [arthrosis of hip]
- M17 Gonarthrosis [arthrosis of knee]
- M18 Arthrosis of first carpometacarpal joint
- M19 Other arthrosis

M40-M43 Deforming dorsopathies

- M40 Kyphosis and lordosis
- M41 Scoliosis
- M42 Spinal osteochondrosis
- M43 Other deforming dorsopathies

M45-M49 Spondylopathies

- M45 Ankylosing spondylitis
- M46 Other inflammatory spondylopathies
- M47 Spondylosis
- M48 Otherspondylopathies
- M49 Spondylopathies in diseases classified elsewhere

M50-M54 Other dorsopathies

- M50 Cervical disc disorders
- M51 Other intervertebral disc disorders
- M53 Otherdorsopathies, not elsewhere classified
- M54 Dorsalgia

M60-M63 Disorders of muscles

- M60 Myositis
- M61 Calcification and ossification of muscle
- M62 Other disorders of muscle
- M63 Disorders of muscle in diseases classified elsewhere

M95-M99 Other disorders of the musculoskeletal system and connective tissue
M95 Other acquired deformities of musculoskeletal system and connective tissue
M96 Postprocedural musculoskeletal disorders, not elsewhere classified
M99 Biomechanical lesions, not elsewhere classified

R50-R69 General symptoms and signs
R51 Headache
R52 Pain, not elsewhere classified

Source:

- ICD-10-GM Version 2014, Internationale statistische Klassifikation der Krankheiten und verwandter Gesundheitsprobleme 10. Revision, German Modification Version 2014, <http://www.dimdi.de/static/de/klassi/icd-10-gm/kodesuche/onlinefassungen/htmlgm2014/>. Access 20.08.2014
- Source: <http://apps.who.int/classifications/icd10/browse/2010/en>

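### The share of prescriptions classed as acute pain has low specificity, so the 2012 to 2014 comparison would understate a real shift from chronic to acute use

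*Protocol*

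**What the plan says.** Section 9.7.2.1 sets three routes by which a prescription can be linked to acute pain. The first is a principal diagnosis documented with the prescription. The protocol explains the other two: "As not for all prescriptions principal diagnoses will be available, additionally the following approaches will be chosen". An Annex 3-ii disease "recorded in a time frame of 2 weeks around the date of prescription, this will be defined as associated diagnosis", and one "recorded in a 12 months history before the date of prescription, this will be defined as co-morbidity". The planned output is "Number and percentage of prescriptions associated with acute pain (principal diagnoses, associated diagnoses and co-morbidities". The chronic-pain counterpart has one route: "Number and percentage of prescriptions associated with chronic pain (only principal diagnoses".

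The same section states: "Principal diagnoses, associated diagnoses and co-morbidities will be analysed separately". It also tabulates prescriptions by diagnosis, from principal diagnoses only.

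The code list is headed "Diseases associated with acute pain, acute pain episodes, acute pain exacerbations (selection". It includes Parkinson disease, multiple sclerosis, all arthrosis groups, spinal deformities and spondylopathies. Section 9.7.2.1 says the Annex 3 codes cover both acute and chronic pain, but the annex as shown has only a product list (i) and the acute-pain list (ii).

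In the pre-post comparison of 9.7.2.4, the only parameter on the pain treated is "Number and percentage of prescriptions with diagnosis associated with acute pain". No route is named and no chronic-pain parameter is listed.

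**The concern.** Section 7 describes a regulatory procedure meant to confine flupirtine to short-term treatment of acute pain and to remove the chronic-pain indication. Section 8 makes the reasons for prescription an aim, and 9.1 sets a pre-post design. Whether use moved from chronic to acute pain is therefore a main question for this study.

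Under the stated rule, a prescription for long-standing knee arthrosis can be classed as acute pain in both years, even if the arthrosis code was entered many months before. Chronic pain has fewer ways of being found. The two categories are neither ascertained alike nor mutually exclusive, and only the broader one is carried into the comparison. A change in prescribing could look much smaller than it was, and confidence intervals would not reveal this.

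**Working it through.** **1. Plan's own figures.** The protocol gives no acute-pain share and no misclassification rate, so there is nothing to reproduce on that point. The study sizes used in step 5 do reproduce from Table 2 (9.5): 11,284 × 0.75 = 8,463 (PCP) and 1,821 × 0.75 = 1,365.75, stated as 1,365 (orthopaedist).

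**2. Code count, Annex 3-ii.** G20–G23, G35, G44 (6) + M15–M19 (5) + M40–M43 (4) + M45–M49 (5) + M50, M51, M53, M54 (4) + M60–M63 (4) + M95, M96, M99 (3) + R51, R52 (2) = 33.

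- Narrow reading of long-standing disease: G20–G23 (4), G35 (1), M15–M19 (5), M40–M43 (4), M45 and M47 (2) = 16; 16/33 = 48%.
- Wider reading, adding M46, M48–M51 and M95 (6): 22; 22/33 = 67%.
- Injury codes: 0. Codes whose listed title marks an acute event: 0.

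The range reflects judgement about titles. It counts codes, not prescriptions.

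**3. Ascertainment side by side.**

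| | Acute pain | Chronic pain |
|---|---|---|
| Principal diagnosis | yes | yes |
| Code within 2 weeks around prescription | yes | no |
| Code in prior 12 months | yes | no |
| Code list in Annex 3 as shown | yes (ii) | none |
| Compared in 9.7.2.4 | yes, route not named | no |

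**4. Effect on the comparison.** Let p be the true acute share, s the chance that a truly acute prescription is flagged acute, and f the chance that a non-acute one is. With s and f the same in both years:

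- observed share = p·s + (1 − p)·f
- observed change = (s − f) × true change
- error in the level = (1 − p)·f − p·(1 − s)

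The documents give none of p, s or f. For illustration, assume a true rise from 40% to 60% and s = 1. At f = 0.50 this gives 0.40 + 0.60 × 0.50 = 0.70 and 0.60 + 0.40 × 0.50 = 0.80.

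| f (assumed) | 2012 | 2014 | Observed change (points) |
|---|---|---|---|
| 0 | 40% | 60% | +20 |
| 0.25 | 55% | 70% | +15 |
| 0.50 | 70% | 80% | +10 |
| 0.75 | 85% | 90% | +5 |
| 0.90 | 94% | 96% | +2 |

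The absence of injury codes means s is probably below 1. That lowers the level, so the net error in the level can have either sign. It does not restore the change: s − f is smaller than 1 − f.

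If the routes were pooled, f would grow. With 30% of non-acute prescriptions flagged by each of three routes, and independence assumed, 1 − 0.7³ = 66%; at 50% each, 1 − 0.5³ = 88%.

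**5. Against random error.** Around 80%, the 95% half-width is 1.96 × √(0.80 × 0.20 / 8,400) = 0.9 points for PCPs and 1.96 × √(0.80 × 0.20 / 1,300) = 2.2 points for orthopaedists. This uses patients as the denominator, ignores repeat prescriptions, and takes whole panels; the incident and prevalent strata are smaller. At f = 0.50 the loss of 10 points of change is well beyond these widths.

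**The case against.** The strongest reply is that the three routes are to be analysed separately and that principal diagnoses are tabulated by code for each period. The 12-month route would then be visible on its own, and arthrosis or multiple sclerosis could be seen in the table. This stands as mitigation. It does not cure the problem: the 2-week route uses the same codes, Annex 3 as shown offers no other list for grouping principal diagnoses, and 9.7.2.4 does not say which route is compared.

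It can also be said that the list deliberately covers acute episodes and exacerbations of underlying disease, as its heading and 9.9 indicate. Some such prescriptions will be truly acute. But the listed codes cannot show an exacerbation, and a code up to a year old cannot show why flupirtine was given.

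Episode length, repeat prescribing and episodes over 14 days are also compared in 9.7.2.4 and do not depend on Annex 3-ii. They bear on prolonged use, though not on indication.

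A reader might infer three stronger claims that the documents do not support:

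- That on-label use is inflated in both years. Chronic pain was still an indication in 2012, and after the review acute pain is only one condition of labelled use (Section 7).
- That the comparison cannot detect a shift. It is attenuated, not abolished, and other tables give partial information.
- That the error favours a finding of good adherence. The net direction of the level is not established, and attenuation would understate an improvement.

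**Conclusion.** The concern holds for the share classed as acute pain. Its definition has low specificity: roughly half to two-thirds of the codes are long-standing diseases, none marks an acute event, and one route reaches back 12 months. Chronic pain is ascertained more narrowly, lacks a code list in Annex 3 as shown, and is absent from the pre-post comparison. A real move from chronic to acute use would be shrunk by the factor s − f. Its value is unknown; the table in the working is illustrative only.

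The attenuation conclusion assumes that s and f are the same in 2012 and 2014. If coding habits changed after the 2013 communication, the distortion could take another form. A statistical analysis plan, not available here, might name the route compared, but the unequal routes, the look-back and the code list are fixed in the protocol. Because this is the only comparison of the pain treated, it should be corrected before it is interpreted.

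**What to change.** - **9.7.2.4:** base the acute-pain comparison on the principal diagnosis and, where that is missing, on the 2-week window. Report the 12-month route only as history, outside the acute numerator. Add a chronic-pain parameter ascertained with the same windows.
- **Annex 3:** add injury and explicit acute-pain codes to the acute list and supply the chronic-pain list. Put long-standing disease codes that cannot show acuity (arthrosis, spinal deformity, spondylopathy, Parkinson disease, multiple sclerosis) in a separate group for underlying chronic condition with acuity undetermined. Moving them all to an exclusive chronic list would create the opposite error by misclassifying true exacerbations. Reconcile the annex references: 9.3 attaches note iii to the indication, while Annex 3 as shown ends at ii.
- **Presentation:** compare acute, chronic, both and undetermined by period, within panel and user stratum.
- **9.9:** state the low specificity of the diagnosis-based indication, which the limitations do not now mention.

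The cost is a revised annex, revised table shells and recoding of data already extracted; no new data are needed. The price in results is a larger undetermined group and a lower acute share.

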Drug utilisation study (DUS) on flupirtine-containing medicinal products.

Retrospective drug utilisation study using patient-level databases to characterise prescribing practices of flupirtine-containing medicinal products during routine clinical use and assess the main reasons for prescription by representative groups of prescribers.

Rationale and background

Due to a rising number of hepatotoxicity reactions during treatment with flupirtine containing products the Co-ordination Group for Mutual Recognition and Decentralised Procedures – Human (CMDh) recommended on 28 June 2013 to restrict the use of oral Flupirtine medicines and suppositories as following:

- treatment of acute (short-term) pain in adults who cannot use other painkillers, such as non-steroidal anti-inflammatory drug (NSAIDs) and weak opioids
- treatment duration limited to not longer than 2 weeks
- after each full week of treatment patients' liver function should be checked
- treatment termination if any signs of liver problems occur
- contraindicated for patients with preexisting liver disease or alcohol abuse problems
- contraindicated for patients taking other medications known to cause liver problems

The recommendations follow a review by the EMA's Pharmacovigilance Risk Assessment Committee (PRAC) which looked into reported liver problems with Flupirtine, ranging from high liver-enzyme levels to liver failure. The PRAC evaluated the available data on liver safety, noting that there were no cases of liver failure or liver transplantation reported in patients who took the medicine for 2 weeks or less. The PRAC also reviewed the available data on the benefits of Flupirtine and concluded that, while there were data from studies in the treatment of acute pain, there were insufficient data to support its use in the treatment of long-term pain.

The CMDh agreed with the PRAC's conclusions and endorsed the PRAC's recommendations on the use of flupirtine-containing medicines. The CMDh position was sent to the European Commission (EC), which endorsed it and adopted a final legally binding decision valid throughout the EU on 5 September 2013.

The reported outcomes were communicated to healthcare professionals by all Germany marketing authorisation holders (MAHs) via a joint Direct Healthcare Professional Communication (DHPC) distributed in July 2013.

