The PRAC initiated a subsequent benefit-risk evaluation and considered that the controlled clinical studies required by the Note for guidance on clinical investigation of medicinal products for treatment of nociceptive pain (CPMP/EWP/612/00, issued 21 November 2002) for long-term treatment of chronic pain are not available for flupirtine-containing medicinal products². Based on the fact of observed liver effects recorded during long-treatment with Flupirtine and on the absence of controlled long-term clinical studies, the PRAC noted that the management of chronic pain is no longer favourable in terms of the benefit-risk balance for flupirtine-containing medicinal products. The PRAC adopted a recommendation on 13 June 2013 under the provisions of article 107i of Directive 2001/83/EC³.

Taking the currently available data into account, the PRAC decided that the benefit-risk balance for flupirtine-containing products is favourable in the treatment of acute pain, subject to implementation of the following risk minimisation measures⁴:

- Limitation of indication to acute pain in adults if treatment with other analgesics (e.g. NSAIDs, weak opioids) is contraindicated.
- Restriction of Flupirtine use to a maximum of two weeks of treatment.
- Contraindication of Flupirtine in patients with pre-existing liver disease or alcohol abuse.
- Contraindication of Flupirtine in patients concomitantly taking other medications which are known to cause Drug Induced Liver Injury (DILI).

- Weekly liver function tests during treatment and discontinuation in the case of abnormal liver function tests or clinical symptoms.

The PRAC imposed a DHPC, which was distributed on 15 July 2013, in order to communicate the outcome of the PRAC/EMA decision to healthcare professionals⁵. The SmPCs for flupirtine-containing medicinal products have been revised accordingly by Lupin in February 2014 and MAHS marketing flupirtine-containing medicinal products in September/October 2013⁶. The educational material was distributed in February 2015.

Patients and prescribers have been provided with joint educational material according to the PRAC request, prepared jointly by all German MAHs. The educational material, the DUS and a PASS protocol are parts of the RMP.

As of 5 September 2013, the European Commission implemented the decision (C(2013) 5788 final) with the majority opinion of the CMD(h) addressed to all member states based on the PRAC's recommendation⁷.

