9.3. Variables

The following variables will be derived from the data sources.

IMS[®] Disease Analyzer – PCP and orthopaedist panels

- Number of prescribing physicians
- Region of office (East/West Germany)
- Number of overall patients in the office
- Number of patients with at least one prescription of flupirtine-containing medicinal product
- Patient characteristics
 - Age
 - Gender
 - Insurance status (private or SHI insured)
 - Indication for Flupirtine exposureⁱⁱⁱ
- Flupirtine exposure
 - Number of Flupirtine prescriptions per patients during the observation period
 - Single use and repeated prescriptions
 - Treatment duration (by physician)
 - Dosage advice (by physician)
 - Prescription length (based on DDD or on physician's advice if available)
 - Co-diagnosis during study period
 - Concomitant prescription of drugs grouped by relevant ATC classesⁱⁱ
- Long-term medications (>14 days) leading to contraindication for Flupirtine
- Diseases contraindicated for NSAIDs and weak opioids
- Liverfunction tests - as far as available within 1 week after Flupirtine exposure

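### NSAID and weak-opioid contraindications are pooled under an either-or rule, so the count is only an upper bound on patients with both recorded, while the protocol's own wording of the restriction and of the variable joins the classes with *and*

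*Protocol*

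**What the plan says.** The abstract (section 4, Rationale and background) gives the restricted indication as "treatment of acute (short-term) pain in adults who cannot use other painkillers, such as non-steroidal anti-inflammatory drug (NSAIDs) and weak opioids". Section 7 restates it among the risk minimisation measures as "Limitation of indication to acute pain in adults if treatment with other analgesics (e.g. NSAIDs, weak opioids) is contraindicated". There the two classes are examples, with no conjunction between them.

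The objectives, in the abstract and in section 8, refer to contraindications to one class *or* the other. Section 9.3 lists the variable as "Diseases contraindicated for NSAIDs and weak opioids". Section 9.7.2.1 searches the history for "medical events referencing to contraindications for NSAIDs or weak opioids (such as myocardial infarction or stroke) for a timeperiod of 12 months prior" to the first prescription and adds: "Only patients with a history of at least 12 months will be included in this analysis". Its output is a single line: "Number and percentage of patients identified as contraindicated of NSAIDs/weak opioid treatment (such as myocardial infarction or stroke". The two example events are not assigned to either class.

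Section 9.7.2.4 carries the measure into the comparison of the two periods as "Number and percentage of patients with any diagnosis of disease contraindicated for NSAIDs or weak opioids". Section 9.7.1 says that parameters suited to comparing the periods on the effect of the risk minimisation measures will also be shown graphically.

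**The concern.** Section 7 lists the limited indication among the risk minimisation measures. Of the six parameters in section 9.7.2.4, only this one bears on whether other analgesics were unavailable to the patient. Under the rule as written, a patient with one diagnosis against NSAIDs and nothing recorded against weak opioids is counted in the same way as a patient with contraindications to both.

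Two things follow. The pooled percentage cannot be set against the abstract's wording of the restriction, because the number of patients with both is not reported and cannot be recovered. A change between 2012 and 2014 also cannot be attributed, since it may come from one class alone. In addition, the protocol joins the classes with *and* in one place and *or* in others for the same variable, so two programmers could build two different indicators from it.

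**Working it through.** **Denominator.** Section 9.5, Table 2, gives patients with at least 12 months of history, which is the group section 9.7.2.1 admits, and then applies a 25% reduction.

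- PCP: 11,284 × 0.75 = 8,463 (stated 8,463).
- Orthopaedist: 1,821 × 0.75 = 1,365.75 (stated 1,365).

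The stated figures reproduce. The text rounds them to "not lower than about 8,400 and 1,300 patients in the DA PCP and orthopaedist panel, respectively".

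**Bounds.** Let pN and pO be the proportions with a recorded contraindication to NSAIDs and to weak opioids, and let B be the proportion with both.

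- Either = pN + pO − B.
- B lies between max(0, pN + pO − 1) and min(pN, pO).
- Excess of either over both = pN + pO − 2B, which is never below |pN − pO|.

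The excess is zero only if the same patients carry both contraindications. Either can therefore never fall below both. This holds whatever the data show.

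**One illustration.** The protocol gives no contraindication prevalences. Assume pN = 30% and pO = 10%.

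- Independent: either = 1 − 0.7 × 0.9 = 37%; both = 0.3 × 0.1 = 3%; excess 34 points, or 2,877 of 8,463 PCP patients and 464 of 1,365 orthopaedist patients.
- Fully nested: either = 30%; both = 10%; excess 20 points.
- No overlap: either = 40%; both = 0%; excess 40 points.

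**Range.** Assume pN from 10% to 40% and pO from 2% to 20%.

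| Overlap | Either | Both | Excess (points) |
|---|---|---|---|
| Independent | 11.8% to 52.0% | 0.2% to 8.0% | 11.6 to 44.0 |
| Greatest possible | 10% to 40% | 2% to 20% | 0 to 38 |
| None | 12% to 60% | 0% | 12 to 60 |

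Under independence the excess is about 980 to 3,720 of 8,463 PCP patients, and 158 to 601 of 1,365 orthopaedist patients. The zero in the second row arises where pN = pO and the patients coincide.

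**Against sampling error.** The 95% half-width is 1.96 × √(p(1 − p)/n). For p from 10% to 50% it is about 0.6 to 1.1 points in the PCP panel and 1.6 to 2.7 points in the orthopaedist panel. It will be wider within the incident and prevalent strata. Under independence, the choice of definition outweighs panel-level sampling error throughout the assumed range.

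**Change between periods.** The change in either equals the change in pN plus the change in pO minus the change in B. Suppose pO stays at 10% and B at 3%, and pN rises from 30% to 35%. The pooled figure then rises from 37% to 35 + 10 − 3 = 42%, while the proportion with both does not move. This shows that the pooled change is ambiguous. It does not show which way, if any, the real comparison is distorted.

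**The case against.** A reader might infer that the study overstates on-label use, or that it reports the most favourable adherence figure possible. The documents do not support that. Nowhere does the protocol call this count on-label use or adherence. The study is descriptive, and the ENCePP checklist (Annex 2, item 3.2) answers No on whether primary and secondary endpoints are specified. The pooled rule gives the highest figure only among ways of combining the same codes. Against patients' true status, the 12-month look-back misses older diagnoses, and section 9.9 concedes that care outside the practice is not recorded. Both pull the count down. A rule requiring both contraindications could lose more, since it needs a recorded code for each class.

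The demand for both contraindications is also not beyond dispute. The abstract introduces the classes with *such as*, and section 7 with *e.g.*, so neither fixes the restriction as exactly two coded contraindications. The *or* in sections 9.7.2.1 and 9.7.2.4 agrees with the objectives; section 9.3 is the exception among the definitions of the variable. The same rule applies in both years, and no bias in the difference between them has been shown.

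Finally, section 9.8 refers to a statistical analysis plan and table shells, which may split the classes.

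Most of this stands and limits the claim. It does not remove the mismatch. The protocol itself fixes the either-or rule and the single output line, and it words the restriction and the variable differently elsewhere.

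**Conclusion.** The point holds in a limited form. As written, sections 9.7.2.1 and 9.7.2.4 yield one pooled count. Read against the abstract's wording, that count is an upper bound on the patients with both contraindications on record. The bound is certain; its looseness is unknown. The 37% against 3%, and the 11.6 to 44.0 points, rest on assumed prevalences and on independence. With the greatest possible overlap, the excess over the same range runs from 0 to 38 points. The net error against true status and the effect on the 2012 to 2014 difference could each go either way. The wording across the abstract and sections 7, 8, 9.3, 9.7.2.1 and 9.7.2.4 is not reconciled. The change should be made because it is cheap and this is the only compared parameter on unavailability of alternatives.

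**What to change.** 1. Reconcile the wording in the abstract (rationale and objectives) and in sections 7, 8, 9.3, 9.7.2.1 and 9.7.2.4, so that one definition of the variable applies throughout and its relation to the restriction is stated.
2. In sections 9.7.2.1 and 9.7.2.4, report four exclusive rows: NSAID contraindication only, weak-opioid contraindication only, both, and neither. Give them by period, panel and incident or prevalent status, from a separate ICD-10 list for each class. State which diagnoses, if any, stand on both lists. The pooled figure is the sum of the first three rows, so nothing now planned is lost.
3. Say that the pooled figure alone will not be interpreted as meeting the restriction. Show the row for both beside it as the one matching the abstract's wording, and state that the 12-month look-back under-records contraindications in every row except *neither*, which it can inflate. Showing all rows leaves the reading of *such as* and *e.g.* open to the regulator.

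The cost is two code lists in place of one, a few extra table rows and a lower percentage in the stricter row. No new data are needed.
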